The GMT induced in group k ($k = 5, 7$, or 8) is NI as compared to the GMT induced in group R3 using a NI margin of $2/3$. Similarly, the GMT induced in group k ($k = 6$) is NI as compared to the GMT induced in group R4 using a NI margin of $2/3$

Statistical method:

Objectives 2a, 2b, 2c and 2d: evaluated only at the primary analysis

The NI analysis on the GMR, in each group g ($g = 5, 7$, or 8) compared to the reference group R3 and in group $k=6$ compared to the reference group R4, will, respectively, be assessed by first constructing the 2-sided $(1 - 2*\alpha)$ % confidence interval for the difference in means (i.e., booster vaccination after Ad26.COV2.S (original virus or leading variant of high consequence or concern*) minus primary vaccination (original strain or leading variant of high consequence or concern*) log10 transformed data) based on the sampling distribution of two independent normal distributions with variances that are unknown but assumed equal.

Let $X_g = \log_{10} Y_g \sim N(\mu_g, \sigma_g)$, normally distributed with true population mean and standard deviation, μ_g and σ_g respectively and where X_g is the log-transformed (log₁₀ scale) virus neutralization assay (VNA) titers for Cohort 2 booster vaccine groups, $g = 5, 6, 7, 8$ (so defined to reflect the hypotheses in Figure 3 Refer to Clinical Trial Protocol (CTP); section 9.1).

Let $X_R = \log_{10} Y_R \sim N(\mu_R, \sigma_R)$, where X_R ($R = R_3$ or R_4) is the log-transformed (log₁₀ scale) virus neutralization assay (VNA) titers for the 2-dose Pfizer BNT162b2 primary vaccination (original strain) (Reference group 3) or the 2-dose Pfizer BNT162b2 primary vaccination (leading variant of high consequence or concern*), if feasible (Reference group 4)

It can be shown that the log-transformed (log₁₀ scale) virus neutralization assay (VNA) titers mean differences between the vaccine groups g , $(\bar{X}_g - \bar{X}_R)$, is equal to the log-transformed (log₁₀ scale) ratio of the corresponding geometric means, i.e., $\log_{10}(GMT_g/GMT_R)$

Hence, back transforming yields, $GMT_g/GMT_R = 10^{(\bar{X}_g - \bar{X}_R)}$ as the geometric mean ratio estimates.

Next, we can construct the $(1 - 2*\alpha)\%$ confidence interval (2-sided) (where $\alpha = 1$ -sided significance level), for the geometric mean ratios, by first constructing the confidence interval on the difference on the means, $(\bar{X}_g - \bar{X}_R)$.

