Assuming unknown equal variances for the population cohort 2 booster vaccine groups g and the reference group, R, and log-transformed (log₁₀ scale) virus neutralization assay (VNA) titers, the (1 - 2* α) % confidence interval (2-sided), (where α = 1-sided significance level), estimate for the population mean differences, is given by,

$$(\overline{X_g} - \overline{X_R}) \pm t_{(1-2*\alpha/2; v_p)} S_p \sqrt{\left(\frac{1}{n_g} + \frac{1}{n_R}\right)}$$

Where the *pooled variance estimate*, $S_p^2 = \frac{(n_g-1)S_g^2 + (n_R-1)S_R^2}{n_g+n_R-2}$ and $v_p = n_g + n_R - 2$ is the degrees of freedom for the t-distribution and $\alpha = 0.025$.

Since log transformation is monotone, back transforming confidence intervals for the difference in means in the log10 scale gives a confidence interval for the ratio of the geometric means. Hence, the lower and upper bounds of the 2-sided (1 - 2 * α)% (i.e., 97.5% since $\alpha = 0.0125$ (1-sided)) confidence interval for the GMT ratios are as follows:

$$((GMT\ Ratio))_{Lower\ Limit} = 10^{\left((\overline{X_g} - \overline{X_R}) - t_{(1-\alpha/2; v_p)} S_p \sqrt{\left(\frac{1}{n_g} + \frac{1}{n_R}\right)} \right)}$$

$$((GMT\ Ratio))_{Upper\ Limit} = 10^{\left((\overline{X_g} - \overline{X_R}) + t_{(1-\alpha/2; v_p)} S_p \sqrt{\left(\frac{1}{n_g} + \frac{1}{n_R}\right)} \right)}$$

If the assumptions of the unknown equal variances for the independent normal distributions of cohort 2 booster vaccine groups g and the reference group, R, do not hold (i.e., test of equality variances shows that the variances are significantly different), then an approximate t-distribution with Satterthwaite approximated degrees of freedom will be used instead (Casella, G & Berger L.R (1990)).

For each of the booster vaccine groups, g comparisons, NI will be demonstrated if

$((GMR\ Ratio))_{Lower\ Limit} > \frac{2}{3}$, where the lower limit corresponds to a 97.5% 2-sided confidence interval.

SAS v 9.4 will be used in implementing the NI comparisons.

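### The Cohort 2 GMR interval is chosen by an unspecified equal-variance pretest; using the Satterthwaite interval throughout is safer and costs almost nothing

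*SAP*

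**What the plan says.** Main SAP section 5.7.1.5.2, Success Criterion 2, compares log10 neutralizing titers in each Cohort 2 booster group with an external BNT162b2 reference. The default interval is "based on the sampling distribution of two independent normal distributions with variances that are unknown but assumed equal". If a "test of equality variances shows that the variances are significantly different", "then an approximate t-distribution with Satterthwaite approximated degrees of freedom will be used instead". The type of variance test and its significance level are not given.

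Non-inferiority needs the lower limit of the GMR interval to exceed 2/3, "where the lower limit corresponds to a 97.5% 2-sided confidence interval". Section 5.7.1.5 adds two further requirements for each objective: the rate criterion, and an estimated GMR above 0.8.

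The reference is about 300 individuals drawn from biobanks or clinical studies (section 4), bled between two weeks and two months after their second dose. The booster groups are trial participants sampled 14 days after an Ad26.COV2.S booster. Sample size is left to protocol section 9.2 (main SAP section 3), so this document gives neither the Cohort 2 group sizes nor the SDs.

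**The concern.** The two groups come from different sources, with different vaccine histories and sampling windows. Equal variance is therefore an assumption that nothing in the design secures. A non-significant variance test does not establish it either, because at moderate differences such a test often misses. The pooled interval then stays in use where it is wrong. With unequal group sizes it is too narrow if the smaller group is the more variable, and too wide if the smaller group is the less variable.

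The rule is also not fully fixed. An analyst could choose among several variance tests and levels, and that choice can change a primary interval. The rule runs separately for each comparison, so objectives 2a, 2c and 2d, which share one reference group, could be judged by different interval types. At stake are the one-sided level of a primary criterion and a data-dependent step that could be avoided.

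**Working it through.** **Inputs from the main SAP**
- Reference size n_R of about 300; GMR margin 2/3; pooled interval by default with Satterthwaite as fallback (section 5.7.1.5.2).
- One-sided level 0.0125. The stated confidence level is reproduced: 1 - 2 × 0.0125 = 0.975. The same section also prints alpha as 0.025 beside the pooled formula. That is a separate notation point; the calculation below uses the 97.5% two-sided level on which the decision rests.

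**Assumptions**
- Booster group size n_g from 100 to 330. The only size hint is for Cohort 1 Group 1, where 110 participants are about 33% of the total (section 5.8.1): 110 / 0.33 ≈ 330.
- SD ratio (booster/reference) near 1; normal log10 titers; a two-sided 5% F test as the variance test.

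**Why the pooled interval misses its level.** Take n_g = 100, n_R = 300, reference SD 1 and ratio 1.15 (1.15² = 1.3225).
- True variance of the difference: 1.3225/100 + 1/300 = 0.01656.
- Variance that the pooled formula estimates: [(99 × 1.3225 + 299)/398] × (1/100 + 1/300) = 1.0802 × 0.01333 = 0.01440.
- The standard error is too small by the factor √(0.01440/0.01656) = 0.933.
- The t quantile 2.25 acts as 2.25 × 0.933 = 2.10, an upper tail of about 0.018 against 0.0125. Simulation gives 0.0183.

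**What the pretest recovers.** At n_g = 100 and ratio 1.15 the 5% F test rejects only 42% of the time (44% at n_g = 110), so the pooled interval is kept in more than half of trials.

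**Simulated one-sided error at true GMR = 2/3.** There were 1,000,000 draws per setting, with simulation standard error √(0.0125 × 0.9875/1,000,000) ≈ 0.0001. Separate runs differ by a few units in the fourth decimal.

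| n_g (n_R = 300) | Two-stage, booster SD 10-15% larger | Two-stage, booster SD 10% smaller |
|---|---|---|
| 100 | about 0.0148 | about 0.0108 |
| 150 | about 0.0139 | about 0.0115 |
| 200 | about 0.013 | about 0.012 |
| 300-330 | 0.0123-0.0128 | 0.0123-0.0128 |

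Satterthwaite throughout stayed at 0.0123-0.0127 in every setting.

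**The unstated test level matters.** At n_g = 100 and ratio 1.15, the two-stage error is 0.0163, 0.0148 or 0.0141 with a 1%, 5% or 10% F test.

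**Power under equal variances** (true GMR set for about 90% power, SD 0.5), two-stage against Satterthwaite:
- n_g = 300: 89.90% v 89.90%.
- n_g = 150: 89.78% v 89.70%.
- n_g = 110: 89.82% v 89.64%.
- n_g = 100: 89.78% v 89.53%.

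When the smaller booster group is the less variable one (n_g = 110, ratio 0.9), Satterthwaite gains power: 89.7% v 88.6%.

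**Where the 0.8 rule takes over.** At a true GMR of 2/3, an estimate above 0.8 is a stricter demand than the interval when 2.24 × SE < log10(0.8 ÷ 2/3) = log10(1.2) = 0.0792. With SE = SD × √(1/n_g + 1/300), the common SD must be below:
- 0.0792/(2.24 × 0.1155) ≈ 0.31 at n_g = 100.
- 0.0792/(2.24 × 0.1000) ≈ 0.35 at n_g = 150.
- 0.0792/(2.24 × 0.0798) ≈ 0.44 at n_g = 330.

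Below these SDs the choice of interval hardly affects the false-positive rate.

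**The case against.** The SAP prespecifies both the trigger and the fallback, so it does not ignore unequal variances or leave a free choice after the data are seen. A reader might infer that the planned rule inflates the type I error of this trial. The document does not support that. Inflation needs a booster group that is both clearly smaller than about 300 and moderately more variable, and no section says either. The reverse SD ratio makes the rule conservative. At the only size hinted at, about 330 and for Cohort 1 only, nothing material happens. The worst figure in the table is about 0.2 percentage points above target and rests on an assumed 5% test. Where SDs are small, the rule on the estimated GMR governs instead.

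All of that stands, and it limits the point to a minor one. Two things survive it. The prespecification is incomplete, because the test and its level are missing. And evaluable numbers can fall below enrolment, since the NI set keeps only baseline-seronegative participants of the per-protocol immunogenicity set (section 4) and out-of-window samples are dropped from that set's tables and graphs (section 5.7.1.1). A variance F test is also sensitive to non-normality, which the LLOQ/2 and ULOQ imputation in section 5.7.1.3 could cause; this was not simulated.

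**Conclusion.** The point holds as a minor improvement. A primary interval is selected by an unnamed, unlevelled variance test in a comparison where equal variance is not assured by design. Under the assumed 5% F test and 300 reference samples, the two-stage error ranges from about 0.011 to 0.015 against 0.0125, depending on group size and on which group is more variable. At 300-330 per group the departure is negligible.

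Two stronger statements should not be made. One is that the variances are in fact unequal: differing sources make equality unsecured, not false. The other is that the change is free: its power cost is very small but not zero when groups are unbalanced. Cohort 2 group sizes, SDs and the level of the variance test are all assumptions here.

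**What to change.** In main SAP section 5.7.1.5.2, state the Satterthwaite (Welch) t interval as the sole method for all Cohort 2 GMR comparisons. Delete the pooled formula and the equality-of-variance test. The method is already the SAP's own fallback, so nothing new is introduced and only wording changes. The downside is a power loss under equal variances of nil at about 300 per booster group, about 0.1 points at 150 and about 0.2 points at 100. It would reach about 0.9 points only if a group were as small as 50.

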5.7.1.5.3. Sensitivity NI Analysis (cohort 1 objectives) – Statistical method

A sensitivity analysis, for the primary objectives 1a, 1c and 1d in cohort 1, will be conducted by pooling the 28 days post-dose 1 VNA data across the three study arms and comparing it to the 14 days post booster VNA data in the study arm of interest. That is, for primary objectives 1a, 1c and 1d by pooling all VNA data in Reference group 1 (R1) and comparing it to each of the groups 1, 3 and 4 (see section 5.7.1.5.1), respectively.

For each vaccination group 1,2 and 3, the pooled and each vaccination group 14 days post booster VNA data will jointly constitute repeated measures data collected at two time points, Day 0 and Day 15 which are correlated by design. Day 0 refers to the day the primary vaccination (cohort 1) was collected. Each vaccination group repeated measures data will be analyzed using appropriate statistical model that accounts for the correlation of the repeated measures data.

For the analysis of each vaccination group repeated measures correlated binary response VNA data, Generalized Estimating Equations (GEEs) (Liang and Zeger (1986)) method will be used. This approach provides a non-likelihood based or quasi-likelihood approach for modeling correlated responses by specifying one of a variety of possible working correlation matrix structures to account for the within-participant correlations. PROC GENMOD in SAS will be used to fit the Generalized Estimating Equation (GEE) model. The random effects model will include the binary response variable as the dependent variable, day as fixed effects and subject as the random (repeated measures) effect. Unstructured variance-covariance matrix will be used in the model and the model will fit the probability that the response variable is equal to '1'.

Within each vaccination group, Day 15 minus Day 0 responder rate differences will be estimated by transforming the model LSMEAN (in SAS) estimates on the logit scale to probability estimates. The associated 2-sided confidence intervals (95% CI for primary objective 1a and 97.5% CI for primary objectives 1c and 1d) will be determined using the bootstrap Percentile Confidence Interval method. A bootstrap sample of 10,000 will be generated with replacement from the original data to accomplish this. NI will then be declared if the within each vaccination group, lower limit of the 2-sided confidence intervals (95% CI for primary objective 1a and 97.5% CI for primary objectives 1c and 1d) of the responder rate (Day 15 – Day 0) difference is greater than -10% (see DPS for some guidance in coding).

Similarly, for the analysis each vaccination group repeated correlated continuous VNA data, Mixed Effects model method will be used. The random effects model will include the continuous log VNA (\log_{10} scale) variable as the dependent variable, day as fixed effects and subject as the random (repeated measures) effect. Unstructured variance-covariance matrix will be used in the model. PROC Mixed (in SAS) will be used to fit the model.

Within each vaccination group, Day 15 minus Day 0 mean differences (\log_{10} scale) and associated 2-sided confidence intervals (95% CI for primary objective 1a and 97.5% CI for primary objectives 1c and 1d) will be determined from the appropriate LSMESTIMATE (in SAS) of the vaccine day fixed effect in the model.

The GMRs (booster/primary) and associated confidence intervals will then be estimated by back transforming the differences in means (\log_{10} scale) and associated confidence intervals, respectively. NI, within a vaccination group, will then be declared if the lower limit of the 2-sided confidence interval (95% CI for primary objective 1a and 97.5% CI for primary objectives 1c and 1d) of the GMR (booster/primary) is greater than 2/3 (see DPS for some coding guidance).

Remark: Sensitivity analysis will only be conducted at the primary analysis.

5.7.1.6. Immunogenicity against the insert**5.7.1.6.1. Humoral assays****5.7.1.6.2. Responder Definition and Data Summary**

For neutralizing and binding antibodies to the reference SARS-CoV-2 strain and variants:

- A sample will be considered positive if the value is strictly greater than the LLOQ ($>\text{LLOQ}$).

Two responder definitions, as defined below, are considered in the study.

5.7.1.6.2.1. Primary Responder Definition (FDA):

- For Pre-booster time points (Day 29): responder if at least one of the following conditions is satisfied:
 - If pre-dose 1 titer $<\text{LLOQ}$, then post-vaccination titer $\geq 4 \times \text{LLOQ}$
 - If pre-dose 1 titer $>\text{LLOQ}$, then post-vaccination titer $\geq 4 \times$ pre-dose 1 titer
- For Post-booster time points: responder if at least one of the following conditions is satisfied:
 - If pre-booster titer $<\text{LLOQ}$, then post-booster titer $\geq 4 \times \text{LLOQ}$
 - If pre-booster titer $>\text{LLOQ}$, then post-booster titer $\geq 4 \times$ pre-booster titer

Note: In the above definitions, "pre-dose 1" refers to the COV3001 dose 1 and "pre-booster" refers to the COV2008 pre-dose 1.

This definition represents the core definition to be used for the NI assessment of the primary objectives and will be applied to outputs related to psVNA, ELISA, and MSD assays.

5.7.1.6.2.2. Exploratory Responder Definition (Janssen, based on other COVID19 studies):

- A post-baseline sample will be considered a responder if at least one of the following conditions is satisfied:
 - If pre-dose 1 titer $<\text{LLOQ}$, then post-booster titer $\geq \text{LLOQ}$
 - If pre-dose 1 titer $>\text{LLOQ}$, then post-booster titer $\geq 4 \times$ pre-dose 1 titer

This definition will be used for exploratory/supplementary analyses to match the responder definition used in other COV studies and will also be applied to outputs related to psVNA, ELISA, and MSD assays.

For SARS-CoV-2 neutralization VNA, the following statistics will be calculated: N, geometric mean and corresponding 95% CI of the actual values, fold increase from baseline.

For the calculation of the geometric mean and its corresponding 95% CI, the arithmetic mean and its corresponding 95% CI are calculated on the \log_{10} transformed values. These values are back transformed to provide the geometric mean and its corresponding 95% CI.

As exploratory analysis, post-booster GMT and responder rate data will be summarized by pre-boost timepoint low vs. high titers (low [≤ 400 ID50] vs. high [> 400 ID50] titers defined based on COV1001 cohort 2a data). An optimal threshold for defining low vs high will also be explored. The R package “OptimalCutpoints” (Lopez-Raton el. al (2014)) could be implemented to determine the optimal threshold.

Actual values will be tabulated and shown as dot plots with dots for participant values, and the corresponding geometric mean and 95% CI per time point for each assay. In addition, GMT plots over time, combining the regimens in one graph (without individual participant dots) will also be generated.

Participant profiles of the actual values over time will be graphically presented.

Reverse distribution curves of the actual values are provided for selected time points.

In the graphs, original values will be displayed on the \log_{10} scale.

Further details and/or updated rules may be provided in the DPS.

For **S-ELISA/MSD (if available)**, the same as above applies.

The ratio of binding (S-ELISA/MSD) to neutralizing antibodies (VNA), will be calculated for each time point, and per matching variant between binding and neutralizing antibody assays. Values $< \text{LLOQ}$ will be imputed with LLOQ for the calculation of the ratios. In addition, the ratio of the fold increase from baseline in binding antibodies (S-ELISA/MSD) to the fold increase from baseline in the VNA will be calculated for each post-baseline time point. Values $< \text{LLOQ}$ will be imputed with LLOQ for the calculation of the fold increase ratios. The following statistics will be calculated and tabulated: N, geometric mean and corresponding 95% CI of the ratio. Graphical displays will also be prepared, showing – for each time point – the geometric mean of the ratio and its 95% CI, together with the individual data points (dot plot).

If a similar assay is performed at different analyzing labs, then separate statistical analyses may be performed.

Scatterplots between humoral assay results will be provided for selected time points. These may include, but are not be limited to:

- Binding antibodies (S-ELISA/MSD) versus neutralizing antibodies (VNA)

If a similar assay is performed at different analyzing labs, then the statistical analyses may distinguish between these and provide separate scatterplots for each analyzing lab versus the other assay of interest. These scatterplots will display the values as analyzed for the geometric mean calculations, with values $< \text{LLOQ}$ imputed with LLOQ (if an LLOQ is defined) and values $> \text{ULOQ}$ imputed with ULOQ (if an ULOQ is defined). The LLOQ and ULOQ cut-off values per assay will be visualized in the scatterplots. Spearman correlation coefficients will also be provided (one per scatterplot).

5.7.1.6.3. Cellular assays

For **ELISpot**, if available (assay not selected yet), at least the following statistics will be calculated: N, median, first and third quartile, minimum and maximum of the actual values. Additional statistics may be calculated and will be detailed in the DPS. The ELISpot in this study is planned to be two single ELISpot, measuring IFN-g and IL-4. In that case, the statistics will be analyzed for each cytokine separately.

For each cytokine, if available, the following may be defined, depending on the assay selected:

- Sample positivity:
 - For IFN-g: a sample will be considered positive if the value is strictly greater than the LOD (>LOD).
 - For IL-4: a sample will be considered positive if the value is strictly greater than the LOD (>LOD).
- Responder:

A post-baseline sample will be considered a responder if at least one of the following conditions is satisfied:

For IFN-g:

- The baseline sample value is less than or equal to the LOD (\leq LOD) and the post-baseline sample is strictly greater than the LOD (>LOD)
- The baseline sample value is strictly greater than the LOD (>LOD) and the post-baseline sample value represents an at least 3-fold (\geq 3-fold) increase from the baseline sample value.

For IL-4:

- The baseline sample value is less than or equal to the LOD (\leq LOD) and the post-baseline sample is strictly greater than the LOD (>LOD)
- The baseline sample value is less than or equal to the LLOQ (\leq LLOQ) and the post-baseline sample is strictly greater than the LLOQ (>LLOQ)
- The baseline sample value is strictly greater than the LLOQ (>LLOQ) and the post-baseline sample value represents an at least 2-fold (\geq 2-fold) increase from the baseline sample value.

The SDTM database will contain the LOD and LLOQ values.

In keeping with the general derivation rules, values <LLOQ are imputed with LLOQ/2 for the calculation of the median and with LLOQ for the calculation of the fold increases from baseline.

ELISpot values available in the database will already be background subtracted. No further background subtraction should be carried out. In case the SDTM data only contain peptide pools 1 and 2, but no combined peptide pool, then the combined peptide pool will be calculated as the sum of both peptide pools.

Tables with the descriptive statistics will be provided.

Participant profiles of the actual values over time will be graphically presented. For the graphs, original values will be displayed on the \log_{10} scale.

For ELISpot, the reported values are spot forming cells per million peripheral blood mononuclear cells (PBMC).

Further details and/or updated rules may be provided in the DPS.

For **ICS, if available (assay not selected yet)**, at least the following statistics will be calculated: N, median, first and third quartile, minimum and maximum of the actual values, number and percentage of participants with a positive sample (if available). Additional statistics may be calculated and will be detailed in the DPS.

It is planned to analyze the following cell populations at the time of the full analysis, depending on the panel of antibodies selected for the ICS assessment. The DPS may provide an updated version of this list.

- CD4+:
 - IFN-g or IL2
 - IFN-g or IL2 NOT TH2
 - IL4 and CD40L
 - IL4 or IL5 or IL13 and CD40L
- CD8+:
 - IFN-g or IL2

The data received from the analyzing lab(s) may contain background subtracted values (“immediately reportable values”; i.e. background subtracted^a percentages of cells expressing the cytokine or cytokine combination). Negative background subtracted values will be imputed with zero prior to further processing.

The data will contain a positivity call for each cell population. Sample positivity should therefore not be further derived at the statistical analysis stage.

Tables will be provided that show the descriptive statistics mentioned above, structured as follows: CD4+/CD8+, peptide pool (as available in the database, e.g.: SARS-CoV2-S, SARS-CoV2-S1, SARS-CoV2-S2), cytokine (combination), and time point.

Participant profiles of the actual values over time will be graphically presented. For the graphs, original values will be displayed on the \log_{10} scale, with values <0.022% imputed with 0.011%

^a Also known as “mock subtracted”

(only for visual representation; calculations will be based on the actual values). The graphs that show individual participant's data will visually differentiate between positive/negative samples (e.g. different symbols and/or different colors).

The reported values are percentage of cells expressing the cytokine(s).

